Appendix 10 Management of Cobimetinib plus Atezolizumab-Associated Adverse Events (Arm A) (cont.)

DERMATOLOGIC TOXICITY

Dermatologic toxicity and rash is associated with cobimetinib and atezolizumab (see Section 5.1.1.3.1) and should be managed according to the guidelines in Table 3.

Although uncommon, cases of severe cutaneous adverse reactions such as Stevens-Johnson syndrome and toxic epidermal necrolysis have been reported with atezolizumab.

Table 3 Guidelines for Managing Atezolizumab and Cobimetinib Rash

Event	Action to Be Taken
Dermatologic toxicity	
General guidance	
 A dermatologist should evaluate persistent and/or severe rash or pruritus. A biopsy should be considered unless contraindicated.
Dermatologic event, Grade 1 or 2	
 Continue atezolizumab and cobimetinib. Initiate supportive care (e.g., antihistamines, topical corticosteroids). If event does not improve, consider treatment with higher-potency topical corticosteroids. For Grade 2 rash, consider referral to dermatologist for evaluation and, if indicated, biopsy. 
Acneiform rash:
 
 Consider topical corticosteroids (e.g., hydrocortisone 2.5%, alclometasone) and oral antibiotics (minocycline, doxycycline, or antibiotics covering skin flora) as clinically indicated.

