Appendix 10 Management of Cobimetinib plus Atezolizumab-Associated Adverse Events (Arm A) (cont.)

Table 3 Guidelines for Managing Atezolizumab and Cobimetinib Rash (cont.)

Event	Action to Be Taken
Dermatologic event, Grade 3	
 • Withhold atezolizumab and cobimetinib. • Refer patient to dermatologist for evaluation and, if indicated, biopsy. • Consider initiating treatment with 10 mg/day oral prednisone or equivalent, increasing dose to 1–2 mg/kg/day if event does not improve within 48–72 hours. • If event resolves to Grade 2 or better within 12 weeks, resume atezolizumab at fixed dose. If not, permanently discontinue atezolizumab and cobimetinib. ^{a, b} • Permanently discontinue atezolizumab and cobimetinib and contact Medical Monitor if event does not resolve to Grade 1 or better within 12 weeks. ^{a, b, c} • If event resolves to Grade 2 or better within 28 days, resume cobimetinib with dose reduced by one level. If not, permanently discontinue cobimetinib. 
Acneiform rash:
 
 • Consider continuation of topical corticosteroids (e.g., 2.5% alclometasone) and oral antibiotics (e.g., minocycline, doxycycline or antibiotics covering skin flora) when restarting cobimetinib.
Dermatologic event, Grade 4	
 • Permanently discontinue atezolizumab and cobimetinib, and contact Medical Monitor. ^c
Stevens-Johnson syndrome or toxic epidermal necrolysis (any grade)	
 • Follow guidelines for atezolizumab in Appendix 11. • Withhold cobimetinib. • If event resolves to Grade 1 or better, resume cobimetinib. 
Permanently discontinue cobimetinib if withheld for >4 weeks or if Stevens-Johnson syndrome or toxic epidermal necrolysis is confirmed.

^a If corticosteroids have been initiated, they must be tapered over ≥ 1 month to ≤ 10 mg/day oral prednisone or equivalent before atezolizumab can be resumed.

^b Atezolizumab may be withheld for a period of time beyond 105 days to allow for corticosteroids to be reduced to ≤ 10 mg/day oral prednisone or equivalent. The acceptable length of the extended period of time must be agreed upon by the investigator and the Medical Monitor.

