^c Resumption of atezolizumab may be considered in patients who are deriving benefit and have fully recovered from the immune-mediated event. Patients can be rechallenged with atezolizumab only after approval has been documented by both the investigator (or an appropriate delegate) and the Medical Monitor.

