Dermatologic event, Grade 2	
 • Continue atezolizumab. • Consider patient referral to dermatologist for evaluation and, if indicated, biopsy. • Initiate treatment with topical corticosteroids. • Consider treatment with higher-potency topical corticosteroids if event does not improve.
Dermatologic event, Grade 3	
 • Withhold atezolizumab for up to 12 weeks after event onset. ^a • Refer patient to dermatologist for evaluation and, if indicated, biopsy. • Initiate treatment with 10 mg/day oral prednisone or equivalent, increasing dose to 1–2 mg/kg/day if event does not improve within 48–72 hours. • If event resolves to Grade 1 or better, resume atezolizumab. ^b • If event does not resolve to Grade 1 or better while withholding atezolizumab, permanently discontinue atezolizumab and contact Medical Monitor. ^c
Dermatologic event, Grade 4	
 • Permanently discontinue atezolizumab and contact Medical Monitor. ^c

Appendix 11

Risks Associated with Atezolizumab and Guidelines for Management of Adverse Events Associated with Atezolizumab (cont.)

Table 9 Management Guidelines for Dermatologic Events (cont.)

Event	Management
Stevens-Johnson syndrome or toxic epidermal necrolysis (any grade)	
Additional guidance for Stevens-Johnson syndrome or toxic epidermal necrolysis:
 
 • Withhold atezolizumab for suspected Stevens-Johnson syndrome or toxic epidermal necrolysis. • Confirm diagnosis by referring patient to a specialist (dermatologist, ophthalmologist, or urologist as relevant) for evaluation and, if indicated, biopsy. • Follow the applicable treatment and management guidelines above. 
If Stevens-Johnson syndrome or toxic epidermal necrolysis is confirmed, permanently discontinue atezolizumab.

^a Atezolizumab may be withheld for a longer period of time (i.e., > 12 weeks after event onset) to allow for corticosteroids (if initiated) to be reduced to ≤ 10 mg/day oral prednisone or equivalent. The acceptable length of the extended period of time must be agreed upon by the investigator and the Medical Monitor.

^b If corticosteroids have been initiated, they must be tapered over ≥ 1 month to ≤ 10 mg/day oral prednisone or equivalent before atezolizumab can be resumed.

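### Appendix 10, Table 3 gives two answers on restarting cobimetinib after a suspected but unconfirmed Grade 4 Stevens-Johnson/TEN event that recovers within 4 weeks

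*Protocol*

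**What the plan says.** Appendix 10, Table 3 of the protocol covers rash and other dermatologic events in Arm A. For cobimetinib its rows say:

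- **Grade 1 or 2:** "Continue atezolizumab and cobimetinib".
- **Grade 3:** withhold both drugs, then "If event resolves to Grade 2 or better within 28 days, resume cobimetinib with dose reduced by one level"; otherwise stop cobimetinib. A further bullet reads "Permanently discontinue atezolizumab and cobimetinib and contact Medical Monitor if event does not resolve to Grade 1 or better within 12 weeks".
- **Grade 4:** both drugs are permanently stopped and the Medical Monitor is contacted. The only exception is footnote c, which begins "Resumption of atezolizumab may be considered in patients who are deriving benefit and have fully recovered from the immune-mediated event" and is silent on cobimetinib.
- **SJS/TEN, any grade:** go to Appendix 11 for atezolizumab; withhold cobimetinib; "If event resolves to Grade 1 or better, resume cobimetinib"; and "Permanently discontinue cobimetinib if withheld for >4 weeks or if Stevens-Johnson syndrome or toxic epidermal necrolysis is confirmed".

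Appendix 11, Table 9, to which the last row points for atezolizumab, starts from suspicion: "Withhold atezolizumab for suspected Stevens-Johnson syndrome or toxic epidermal necrolysis". It labels its SJS/TEN instructions as additional and sends the site back to the graded rows as well, so for atezolizumab the Grade 4 stop still applies. Appendix 10 has no matching line for cobimetinib.

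**The concern.** The SJS/TEN row carries its own complete set of cobimetinib instructions and is marked as applying at any grade, yet Table 3 does not say whether it replaces the graded rows or adds to them. For most events the choice matters little or leads to the more cautious action. At Grade 4 it decides whether the drug is stopped or restarted. A site that follows the SJS/TEN row literally would restart cobimetinib after a skin reaction for which the row directly above requires a permanent stop, and that row names no reduced dose. Atezolizumab would meanwhile be permanently stopped under Appendix 11. What is at stake is the safety of an individual patient, not the trial's inference.

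**Working it through.** There is no statistical figure to reproduce. The check applies both sets of rows to the same event and then looks for a rule that ranks them.

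**Step 1: which events the resume line can reach.** A confirmed event always stops under the SJS/TEN row. The resume line therefore has meaning only for suspected events that are not confirmed. Such events are within scope, since Appendix 11 opens on suspicion.

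**Step 2: unconfirmed events, cobimetinib only.** The two hold limits are equal: 4 weeks × 7 = 28 days.

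| Path | Graded row | SJS/TEN row | Result |
|---|---|---|---|
| Grade 1–2 | Continue | Withhold | SJS/TEN row more cautious |
| Grade 3, Grade 1 or better within 28 days | Resume one level lower (60 − 20 = 40 mg from full dose) | Resume, dose not stated | Dose gap only |
| Grade 3, settles at Grade 2 by 28 days | Resume one level lower | Keep withholding, stop after 4 weeks | SJS/TEN row more cautious |
| Grade 3, not Grade 2 or better by 28 days | Stop | Stop | Agree |
| **Grade 4, Grade 1 or better within 4 weeks** | **Permanent stop** | **Resume, dose not stated** | **Conflict; SJS/TEN row less cautious** |
| Grade 4, not Grade 1 or better within 4 weeks | Stop | Stop | Agree |

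Two paths agree, one has a dose gap, two differ in the cautious direction, and one (Grade 4 with recovery) gives opposite outcomes with the SJS/TEN row the looser: 2 + 1 + 2 + 1 = 6.

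**Step 3: is there a tie-break for cobimetinib?**

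- Footnote c to Table 3 concerns atezolizumab only.
- The linking rule in Appendix 11, Table 9 concerns atezolizumab only, and Appendix 10 imports it for that drug only.
- Section 5.1.5.1 sends specific events to Appendix 10 without ranking the rows there. Its general table would restart cobimetinib at 40 mg after a first Grade 3 or Grade 4 event.
- Section 4.6.2 makes permanent discontinuation mandatory where the Appendix 10 guidelines require it. That favours the Grade 4 row, but whether Appendix 10 requires it depends on which row governs.
- The Appendix 10 rule on holds longer than 28 days does not reach an event that recovers sooner.

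None of these ranks the rows for cobimetinib.

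**Step 4: how often.** The conflict needs four conditions together: Grade 4, SJS/TEN suspected, SJS/TEN not confirmed, and recovery to Grade 1 or better within 4 weeks. The documents give no rate for this. Section 1.3.5.1 lists no SJS/TEN among the Grade 3 or higher events in 22 melanoma patients given the combination. Single-patient events appear in that list (1/22 = 4.5%, shown as 5%). The exact two-sided 95% upper limit for 0 of 22 is 1 − 0.025^(1/22) = 15.4%. That limit refers to any SJS/TEN, so it says almost nothing about this much narrower path. Appendix 10 calls such reactions uncommon.

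**The case against.** The best defence has four parts.

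**A row named for a diagnosis overrides the general rows.** This is convincing at Grades 1 to 3. Withholding on suspicion of SJS/TEN, while continuing through ordinary mild rash, is what one would expect. Appendix 11 uses the same layout for myasthenia gravis and Guillain-Barré syndrome below its graded neuropathy rows. A reader might count three contradictions in Table 3. The documents do not support that, because in two of them the specific row is simply stricter. The Grade 3 row's own tension between Grade 2 and Grade 1 as the recovery target is a separate matter. At Grade 4 the same argument makes suspicion of a graver diagnosis, later not confirmed, the reason for a restart that the ordinary Grade 4 row refuses.

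**Section 4.6.2 and the word withhold both point to stopping.** A drug already permanently discontinued is no longer being withheld, so each reading taken alone gives one answer. This stands. The table does not issue two simultaneous orders; it leaves open which order applies.

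**The missing dose has a default.** Section 5.1.5.1 supplies 40 mg after a first event, which partly fills the gap. A reader might also infer that cobimetinib is treated more leniently after Grade 4 than after Grade 3. That compares the SJS/TEN row at one grade with the ordinary row at the other. Under the SJS/TEN row alone, the two grades are treated alike.

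**Oversight would catch it.** Grade 4 events are reportable as serious (Section 5.3.3), and rash of Grade 3 or higher is reportable within 24 hours (Section 5.2.3). Appendix 11 also requires contact with the Medical Monitor at Grade 4. These are real safeguards and lower the risk, but they do not correct the instruction that the site reads.

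**Conclusion.** The point holds for one path: suspected SJS/TEN, Grade 4, not confirmed, and recovered to Grade 1 or better within 4 weeks. There, the Grade 4 row and a literal reading of the SJS/TEN row give opposite outcomes for cobimetinib, and no text ranks them. The weight of the protocol favours stopping, but a site has to infer that. The differences at lower grades are not errors.

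It would go too far to infer that the protocol bars any cobimetinib restart after Grade 4. The general table in Section 5.1.5.1 allows one, and the inconsistency lies within the dermatologic table. Nor does the point affect sample size, type I error or any efficacy analysis.

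The number of patients is unknown and expected to be very small. It is limited to Arm A patients still taking cobimetinib, since SAP Version 3 (Section 2.5) states that the study will be terminated early. The reading assumes that the SJS/TEN row opens on suspicion and that an event is assigned to a row by its worst grade. On that basis this is a minor patient-safety correction, worth making because a misreading could matter greatly to one patient.

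**What to change.** In the SJS/TEN row of Appendix 10, Table 3, keep the pointer to Appendix 11, the instruction to withhold cobimetinib, and the permanent stop after more than 4 weeks or on confirmation. Replace only the resume bullet, with:

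> If the event was Grade 4, permanently discontinue cobimetinib as in the Grade 4 row, whether or not SJS/TEN is confirmed. If it was Grade 3 or lower, is not confirmed, and resolves to Grade 1 or better within 4 weeks, resume cobimetinib, reduced by one dose level after Grade 3 or intolerable Grade 2 (Section 5.1.5.1, Table 3).

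The Grade 4 rule and the dose step both come from text already in the protocol. The cost is one bullet in one table, by amendment or site letter, with no change to data collection or analysis.

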Appendix 10 Management of Cobimetinib plus Atezolizumab-Associated Adverse Events (Arm A) (cont.)

PULMONARY EVENTS

Pneumonitis is associated with atezolizumab and cobimetinib (see Section Section 5.1.1.1.5 and should be managed according to the guidelines in Table 4.

Table 4 Guidelines for Managing Atezolizumab– and Cobimetinib–Associated Pulmonary Toxicity

Event	Action to Be Taken
Pulmonary events	
General guidance	
 Mild-to-moderate events of pneumonitis have been reported with atezolizumab and cobimetinib. All pulmonary events should be thoroughly evaluated for other commonly reported etiologies such as pneumonia/infection, lymphangitic carcinomatosis, pulmonary embolism, heart failure, chronic obstructive pulmonary disease, or pulmonary hypertension. For events concerning for pneumonitis, consider comprehensive infectious evaluation including viral etiologies.
Pneumonitis, Grade 1 (asymptomatic)	
 Continue atezolizumab and cobimetinib. Re-evaluate on serial imaging. Consider patient referral to pulmonary specialist.
Pneumonitis, Grade 2	
 Withhold atezolizumab and cobimetinib. Refer patient to pulmonary and infectious disease specialists and consider bronchoscopy or BAL. If bronchoscopy is consistent with immune-mediated etiology, initiate treatment with 1–2 mg/kg/day oral prednisone or equivalent. Resume atezolizumab and cobimetinib if event resolves to Grade 1 or better within 12 weeks.^{a, b} Permanently discontinue atezolizumab and cobimetinib and contact Medical Monitor if event does not resolve to Grade 1 or better within 12 weeks.^{a, b, c} For recurrent events, treat as a Grade 3 or 4 event.
Pneumonitis, Grade 3 or 4	
 Permanently discontinue atezolizumab and cobimetinib.^c Refer patient to pulmonary and infectious disease specialists and consider bronchoscopy or BAL. If bronchoscopy is consistent with immune-mediated etiology, initiate treatment with 1–2 mg/kg/day oral prednisone or equivalent. If pulmonary event does not improve within 48 hours or worsens, consider adding an immunosuppressive agent (e.g., infliximab, cyclophosphamide, IVIg, or mycophenolate). If event resolves to Grade 1 or better, taper corticosteroids over ≥ 1 month.

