5.1.5.3 Management of Cobimetinib- and Atezolizumab-Specific Adverse Events (Arm A)

Toxicities associated or possibly associated with cobimetinib plus atezolizumab treatment should be managed according to standard medical practice.

For management of cobimetinib- and atezolizumab-specific toxicities, including IRRs, gastrointestinal toxicity, dermatologic toxicity, hepatotoxicity, pulmonary toxicity, potential eye toxicity, reductions in LVEF from baseline, rhabdomyolysis, elevated CPK, and hemorrhage, see [Appendix 10](#).

Guidelines for management of patients who experience atezolizumab-associated or possibly associated adverse events, including infusion-related reactions and immune-mediated reactions (e.g., pulmonary, hepatic, gastrointestinal, endocrine, ocular, myocarditis, pancreatic, dermatologic, neurologic, meningoencephalitis, and renal events) are provided in [Appendix 11](#).

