Dyspnea, cough, fatigue, hypoxia, pneumonitis, and pulmonary infiltrates have been associated with the administration of atezolizumab. Patients will be assessed for pulmonary signs and symptoms throughout the study and will also have computed tomography (CT) scans of the chest performed at every tumor assessment.

All pulmonary events should be thoroughly evaluated for other commonly reported etiologies such as pneumonia or other infection, lymphangitic carcinomatosis, pulmonary embolism, heart failure, chronic obstructive pulmonary disease, or pulmonary hypertension. Management guidelines for pulmonary events are provided in [Table 1](#).

Appendix 11

Risks Associated with Atezolizumab and Guidelines for Management of Adverse Events Associated with Atezolizumab (cont.)

Table 1 Management Guidelines for Pulmonary Events, Including Pneumonitis

Event	Management
Pulmonary event, Grade 1	
 • Continue atezolizumab and monitor closely. • Re-evaluate on serial imaging. • Consider patient referral to pulmonary specialist.
Pulmonary event, Grade 2	
 • Withhold atezolizumab for up to 12 weeks after event onset.^a • Refer patient to pulmonary and infectious disease specialists and consider bronchoscopy or BAL. • Initiate treatment with 1–2 mg/kg/day oral prednisone or equivalent. • If event resolves to Grade 1 or better, resume atezolizumab.^b • If event does not resolve to Grade 1 or better while withholding atezolizumab, permanently discontinue atezolizumab and contact Medical Monitor.^c • For recurrent events, treat as a Grade 3 or 4 event.
Pulmonary event, Grade 3 or 4	
 • Permanently discontinue atezolizumab and contact Medical Monitor.^c • Bronchoscopy or BAL is recommended. • Initiate treatment with 1–2 mg/kg/day oral prednisone or equivalent. • If event does not improve within 48 hours after initiating corticosteroids, consider adding an immunosuppressive agent. • If event resolves to Grade 1 or better, taper corticosteroids over ≥ 1 month.

BAL = bronchoscopic alveolar lavage.

- ^a Atezolizumab may be withheld for a longer period of time (i.e., > 12 weeks after event onset) to allow for corticosteroids (if initiated) to be reduced to ≤ 10 mg/day oral prednisone or equivalent. The acceptable length of the extended period of time must be agreed upon by the investigator and the Medical Monitor.

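### For Arm A pneumonitis at Grades 2 to 4, Appendix 10 ties the start of corticosteroids to a bronchoscopy finding and Appendix 11 does not, and the protocol does not say which table prevails

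*Protocol*

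**What the plan says.** Appendix 10 covers adverse events of the combination in Arm A. Its text on pulmonary events says that pneumonitis is associated with both drugs "and should be managed according to the guidelines in Table 4". In that table the Grade 2 row and the Grade 3 or 4 row carry the same two lines. The first is "Refer patient to pulmonary and infectious disease specialists and consider bronchoscopy or BAL". The second is "If bronchoscopy is consistent with immune-mediated etiology, initiate treatment with" oral prednisone, or an equivalent, at a stated dose.

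Appendix 11 covers events associated with atezolizumab. Its Table 1 is titled "Management Guidelines for Pulmonary Events, Including Pneumonitis". At Grade 2 and at Grade 3 or 4 it says "Initiate treatment with 1–2 mg/kg/day oral prednisone or equivalent", with no condition attached. Bronchoscopy or lavage is to be considered at Grade 2. At Grade 3 or 4 the line is "Bronchoscopy or BAL is recommended".

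Section 5.1.5.3, headed for Arm A, points to both. One sentence begins "For management of cobimetinib- and atezolizumab-specific toxicities, including IRRs, gastrointestinal toxicity, dermatologic toxicity, hepatotoxicity, pulmonary toxicity" and ends by referring to Appendix 10. The next sends events associated or possibly associated with atezolizumab to Appendix 11, and lists pulmonary events among its examples. Section 4.4.3.1 says that systemic corticosteroids are recommended, at the investigator's discretion, for specific events associated with atezolizumab, and refers to Appendix 11 for details.

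**The concern.** An investigator treating an Arm A patient with Grade 2 or worse pneumonitis is directed to two tables. One starts corticosteroids only on a bronchoscopy finding. The other starts them on the grade of the event. If no bronchoscopy is done, the first table gives no instruction to start and the second does.

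Pneumonitis is an adverse event of special interest (Section 5.2.3) and is listed as a potential overlapping toxicity of the two Arm A drugs (Section 5.1.3), so the same event can readily fall under both tables. The protocol plans about 160 centers (Section 9.4), and sites could follow either one. There is also a consequence for study treatment. The footnotes to both tables require corticosteroids, once begun, to be tapered over at least a month before atezolizumab may resume. Whether they were begun therefore bears on how long atezolizumab is interrupted after a Grade 2 event.

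**Working it through.** The plan states no figure on this point, so the check is a comparison of the two tables and of the text that says when each applies.

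**Rows side by side**

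| Item | Appendix 10, Table 4 | Appendix 11, Table 1 |
|---|---|---|
| Bronchoscopy, Grade 2 | To be considered | To be considered |
| Bronchoscopy, Grade 3 or 4 | To be considered | Recommended |
| Corticosteroid start, Grade 2 | If bronchoscopy fits an immune-mediated cause | No condition |
| Corticosteroid start, Grade 3 or 4 | Same condition as Grade 2 | No condition |
| If bronchoscopy is not done | Silent on starting | Start instruction still applies |
| Dose where started | 1–2 mg/kg/day prednisone or equivalent | The same |

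**Outcome by patient type, Grades 2 to 4**

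1. Bronchoscopy done and consistent with an immune-mediated cause: both tables say to start, at the same dose. There is no conflict.
2. Bronchoscopy not done: the Appendix 10 condition is not met, so that table gives no instruction to start. Appendix 11 gives one. The instructions differ.
3. Bronchoscopy done and not supporting an immune-mediated cause: Appendix 10 again gives no instruction to start. Appendix 11 still does, provided that the event is regarded as at least possibly associated with atezolizumab. The instructions differ on that proviso.

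Grade 1 is not affected, because neither table calls for corticosteroids there.

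**Does attribution separate the tables?** Not reliably. Table 4 of Appendix 10 is itself written for toxicity of both drugs, and the Section 5.1.5.3 reference to Appendix 11 takes in events only possibly associated with atezolizumab. A pneumonitis in a patient receiving both drugs can meet both descriptions.

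**Is there a rule of precedence?** The opening note of Appendix 10 refers the reader to Appendix 11 for atezolizumab-associated events but does not say which governs where they differ. Elsewhere Appendix 10 hands over expressly to Appendix 11: for infusion-related reactions and cytokine-release syndrome, for Stevens-Johnson syndrome or toxic epidermal necrolysis, and for immune-mediated ocular toxicity. The pneumonitis rows contain no such handover.

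**Is Appendix 10 complete on its own?** Not at Grade 3 or 4. That row goes on to a 48-hour check for improvement before further immunosuppression, and to a corticosteroid taper. The taper presupposes that corticosteroids were started. Appendix 11 counts the 48 hours from that start, whereas Appendix 10 does not say from when they run.

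**The case against.** The strongest reply is that the gap is narrow and other text largely fills it. Appendix 10 does not forbid corticosteroids without bronchoscopy. Section 4.4.3.1 leaves their use to the investigator's discretion, and Section 5.1.5.3 invokes standard medical practice. The Appendix 11 footnotes speak of corticosteroids as something that may or may not have been begun. An investigator who starts them without bronchoscopy breaches neither table. The difference also has a plausible reason: with two drugs that can each cause pneumonitis, Appendix 10 asks for evidence of an immune-mediated cause. Most other actions agree. Both tables withhold atezolizumab at Grade 2, discontinue it permanently at Grade 3 or 4, consider further immunosuppression if there is no improvement at 48 hours, and taper over at least a month.

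Much of this stands, and it rules out three stronger readings that a reader might infer:

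- That the tables direct opposite treatment. They do not: one is silent where the other instructs.
- That every Grade 2 to 4 pneumonitis in Arm A is affected. It is not, because the tables agree when bronchoscopy supports an immune-mediated cause.
- That severity data would vary by site as a result. The documents give no support for this, because severity is graded by NCI CTCAE v4.0 (Section 5.3.3) whatever triggers corticosteroids.

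The reply does not remove the difference itself. Discretion and standard practice apply to both tables alike, so they cannot tell a site which of two explicit triggers the protocol intends.

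**Conclusion.** The point holds in a limited form. It is an inconsistency between two sets of safety instructions, confined to Arm A patients with Grade 2, 3 or 4 pneumonitis who have no bronchoscopy, or whose bronchoscopy does not support an immune-mediated cause. For the second group it also assumes that the event is still treated as possibly associated with atezolizumab.

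The number of such patients cannot be derived. The documents give no pneumonitis rate for cobimetinib plus atezolizumab and no rate of bronchoscopy. Section 5.1.1.1.5 reports 1.6% at all grades for cobimetinib plus vemurafenib, with no Grade 3 or higher events, but that regimen contains no atezolizumab. Purely as an assumption, a pneumonitis rate of 1% to 5% in the 225 planned Arm A patients gives 0.01 × 225 = 2.25 to 0.05 × 225 = 11.25, or about 2 to 11 patients. A reader might take that as the number affected. It would count every case at the assumed rate, including those in which the tables agree, so the affected group would be no larger than this and probably smaller.

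Nothing here touches the sample size, power or type I error. SAP Section 2.5 says that the study is to be terminated early, which limits how many further patients the wording can reach. It remains worth correcting, because it concerns an event of special interest and the remedy is wording only.

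**What to change.** Reconcile the Grade 2 and the Grade 3 or 4 rows of Appendix 10, Table 4 and Appendix 11, Table 1, together with Section 4.4.3.1, so that one stated trigger for corticosteroids applies to Arm A pneumonitis. The text should say what applies when bronchoscopy is not performed and when it does not support an immune-mediated cause. Alternatively, state in Section 5.1.5.3 or in the Appendix 10 pneumonitis rows which table prevails, as Appendix 10 already does for other events. In either case, the Appendix 10 Grade 3 or 4 row should say from when its 48 hours run. The choice of clinical rule belongs to the sponsor's clinical and safety experts.

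The cost is amendment wording. No analysis, data collection or sample size changes.
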